#### 6.2.3 Post-Entry Evaluations

Post-entry evaluations occur after the study entry visit and vaccination #1 administration at week 0. Study visits are scheduled as indicated in the SOE.

The visit window for the post-entry evaluations is  $\pm 14$  days.

Due to the feasibility challenges posed by the COVID-19 situation, starting 03/16/20, the visit window is broadened from  $\pm 14$  days to -14 days to +60 days. The broadened visit window is applicable to visits scheduled to occur before 04/30/20. This will be reviewed again at a later date to see if the 04/30/20 date should be extended (to include visits occurring after 04/30/20), and/or if the visit windows themselves need to be extended further. **See the update below.**

**Upon further review, the visit window is broadened from  $\pm 14$  days to -14 days to +180 days for visits that were planned to occur before 07/15/20. While +180 days is allowed, sites are encouraged to schedule the applicable visits within +90 days.**

The week 24 and week 26 visits should remain separate and coordinated to be as close to 2 weeks apart as feasible, but can be up to 60 days apart. Thus, if the week 26 visit has to be delayed, it is better to postpone the week 24 visit until the week 26 visit can occur 2 weeks later, or as close to that interval as possible.

NOTE A: The deferred study vaccinations #2, #3, and #4 should be performed within 14 days from the time of the previously scheduled week 4, week 12, and week 24 visits, respectively (see [section 6.3.10](#)).

NOTE B: After study entry, administration of non-HIV vaccines must occur more than 2 weeks prior to the scheduled study vaccination #2 (week 4), #3 (week 12), and #4 (week 24) injections.

#### Study Completion Evaluations

The week 48 evaluations will be completed as the participant's final on study visit.

For week 48 visits after 03/16/20, the visit can be a "hybrid" visit, with safety data (AEs) and clinical assessment data per section 6.3.4 (Clinical Assessments, Concomitant Medications/ARV Medications) collected remotely, and the actual clinic visit being dedicated to the lab draw.

This Primary Statistical Analysis Plan (SAP) describes the primary and secondary outcome measures and general analytic approaches of ACTG A5369 that will be included in the primary manuscript or submitted to ClinicalTrials.gov. It has been developed to facilitate discussion of the statistical analysis components amongst the study team; and to provide agreement between the study team and statisticians regarding the statistical analyses to be performed and presented in the Primary Statistical Analysis Report (SAR). Detailed outlines of tables, figures, and coding descriptions that will be included in the Primary SAR are included in the Analysis Implementation Plan (AIP). A separate SAP for Other Objectives will be developed when results for the Primary and Secondary Objectives are known, and analyses will be presented in a separate report. Data for the Primary SAR will be downloaded once the last participant has completed 48 weeks of follow-up, all queries have been resolved, and the database frozen for analysis. The Primary SAR will be used for submission of results to ClinicalTrials.gov. Results for primary outcomes are required to be submitted within one year of the primary completion date (PCD), which is the date that the final participant is examined for the purposes of final collection of data for all of the primary outcomes. The primary immunogenicity outcome is measured at 26 weeks of participant follow-up, and the primary safety outcome data collection is completed at 48 weeks of follow-up. Thus, the PCD of this study is based on 48 weeks of follow-up. Results for secondary outcome measures for this study are due at the same time.

1.1 Summary of Key SAP Updates

| Version | Changes Made | Effective Date |
|---------|--|----------------|
| 1.0 | Original Version | 8/23/2018 |
| 1.0 | Protocol Amendment Review (V1.0, LOA #1) [name] | 3/28/19 |
| 1.0 | Protocol Amendment Review (V1.0, LOA#2) [name] | 4/16/19 |
| 2.0 | Per CM #2, due to the COVID-19 situation, the visit window is broadened from ± 14 days to -14 days to +60 days, starting from 03/16/20. Per LOA#3, the visit window is further broadened from ± 14 days to -14 days to +180 days. | 09/10/20 |

2 Study Overview

2.1 Study Design

A5369 is a phase I/IIa, randomized, double-blind, placebo-controlled study that will evaluate the safety, immunogenicity, and preliminary assessment of efficacy of a novel vaccine encoding “conserved elements” (CE) of the HIV-1 Gag core protein, p24Gag, as a therapeutic vaccine in HIV-1 infected persons on antiretroviral therapy (ART) with the aim to induce potent virus-specific cytotoxic T lymphocytes (CTL) responses. The primary efficacy outcome will be based on HIV-specific immunologic assays at baseline and week 26.

Duration

Participants will be on study for a total of 48 weeks.

Sample Size The target sample size of 40 (20 p24CE; 10 full length Gag; 10 placebo) for the randomized arms is selected to detect a 0.54 difference in the probability that a participant has increased CE responses (0.64 for p24CE vaccine and 0.10 for placebo) between arms based on a two-sided Fisher's exact test with 80% power, 5% alpha level, and 10% inflation of the estimated sample size for loss-to-follow-up or unusable laboratory specimens. The study also has approximately 80% power to detect a difference of 0.85 versus 0.30 when comparing the p24CE and full-length Gag vaccine arms.

Population

HIV-infected individuals receiving ART with plasma HIV-1 RNA <50 copies/mL for at least 2 years (one “blip” allowed), current CD4 T cell counts >500 cells/mm³, and nadir CD4 T cell counts >350 cells/mm³ (by documentation or candidate recall).

Randomization and Stratification

Participants will be randomized 2:1:1 to the p24CE/full-length Gag DNA vaccine arm versus full-length Gag DNA vaccine arm versus placebo arm using the permuted block method.

Randomization will be stratified by indication of willingness to have the leukapheresis procedure at study screening. The active vaccines/placebo will be administered by intramuscular injection/electroporation.

Regimen

Arm 1: p24CE/full-length Gag DNA Vaccine Arm

p24CE1/2 pDNA 4 mg administered by injection/electroporation at week 0 and week 4. Then p24CE1/2 pDNA 2 mg admixed with full-length p55gag pDNA 2 mg administered by one injection/electroporation at week 12 and week 24.

Arm 2: Full-length Gag DNA Vaccine Arm

Full-length p55gag pDNA 4 mg administered by one injection/electroporation at week 0, week 4, week 12 and week 24

Arm 3: Placebo Arm

Placebo (Sodium Chloride for Injection, USP 0.9%) 1 ml administered by one injection/electroporation at week 0, week 4, week 12 and week 24.

Analysis will be performed in a superiority framework, comparing between arms the change in the number of CEs with a CD4 and/or CD8 T cell response from baseline to week 26.

Major change of the study follow-up

Due to the feasibility challenges posed by the COVID-19 situation, Clarification Memo #2 was issued to broaden the visit window from ± 14 days to -14 days to +60 days, starting from 03/16/20. On April 8 2020, after further review, Letter of Amendment #3 was then issued to further broaden the visit window from +60 days to +180 days but sites were still encouraged to schedule the applicable visits within +90 days.

2.2 Hypothesis

We hypothesize that the administration of p24CE Gag DNA vaccine followed by p24CE DNA + full-length Gag DNA vaccine boost to HIV-infected persons on antiretroviral therapy (ART) will focus newly induced immune responses to immunogenic conserved epitopes of Gag and away from decoy variable epitopes, compared to the administration of full-length Gag DNA vaccine alone, and compared to placebo. We will also measure safety and effects on the latent cell reservoir of HIV-1 in the study. The vaccine regimes will be safe and well tolerated.

2.3 Study Objectives

This Primary SAP addresses the following primary and secondary objectives listed in the study protocol. The remaining study objectives in the protocol will be addressed in subsequent analysis plans.

2.3.1 Primary Objective

1. To compare the additional number of p24CEs recognized by a CD4 and/or CD8 T cell response in participants at each study arm at week 26 compared to baseline
2. To evaluate the safety of the p24CE/full-length Gag DNA vaccine and the full-length Gag DNA vaccine in HIV-infected persons receiving ART.

2.3.2 Secondary Objectives

1. To compare the percent of individual study participants in each study arm with a CD4 and/or CD8 T cell response to an increased number of conserved elements (CEs) at week 26 compared to baseline.
2. To compare the percent of individual study participants in each study arm with a CD4 T cell response to an increased number of CEs at week 26 compared to baseline.
3. To compare the percent of individual study participants in each study arm with a CD8 T cell response to an increased number of CEs at week 26 compared to baseline.
4. To compare the change in total magnitude of CD4 T cell responses against each CEs added together across study arms.
5. To compare the change in total magnitude of CD8 T cell responses against each CEs added together across study arms.

2.4 Interim Monitoring

The study will undergo interim review at least annually by an independent ACTG-appointed Study Monitoring Committee (SMC). The SMC will review accrual, baseline characteristics, conduct of the study (including premature treatment and study discontinuations), data completeness, and AEs by treatment arm. The first interim review will occur approximately 6 months after the enrollment of the first study participant, or after 20 participants enroll, whichever occurs first. An

interim review may also be convened if a concern is identified by the DAIDS clinical representative, the study chairs, or study statisticians in consultation with the team.

NOTE: The pre-specified study suspension rule is

If at any time during the study:

- Two or more participants experience a primary safety outcome that is possibly or probably related to study treatment (as judged by the core team, blinded to treatment arm), or
- One or more participants experience a primary safety outcome that is definitely related to study treatment or that is Grade 4 or death and possibly or probably related to study treatment (as judged by the Core Team, blinded to treatment arm), or
- Two or more participants experience a viral load rebound plasma HIV-1 RNA >1,000 copies/ml confirmed by a second consecutive reading,

then enrollment into the study will be temporarily suspended and the Study Monitoring Committee (SMC, unblinded to treatment assignment) will be asked to review all safety data; review the relation to study treatment of the event(s) thought by the blinded Core Team to be a primary safety outcome; and recommend how the study should proceed with respect to resuming enrollment and continuing study treatment.

Pending full SMC review, the protocol team will decide, in consultation with the SMC chair or designee, whether to continue study treatment for subjects already enrolled.

3 Outcome Measures

Per protocol Section 10.2.1, the primary outcome measures are as follows

3.1 Primary Outcome Measures

3.1.1 Immunogenicity

The number of CEs with a CD4 and/or CD8 T cell response at week 26 compared to baseline in an individual study participant. A CE response (for a participant at a given time point) is defined by a criterion (Horton et al., J Immunol Methods. 2007) that uses Fisher's exact test to compare the proportion of peptide-stimulated CD4 and/or CD8 T cells that are cytokine positive to the proportion that are cytokine positive in the unstimulated sample (negative control), and applying a stringent p-value of 10e-5 as a cutoff.

NOTE: The number of CEs with a CD4 and/or CD8 T cell response will be provided by [name] lab.

NOTE: For this primary outcome, we will sum the CD4 and CD8 responses.

3.1.2 Safety

Occurrence of at least one \geq Grade 3 adverse event (AE, see definition of AE in protocol Section 7.1) except injection site pain or tenderness of less than 48 hours duration, that is possibly,

probably, or definitely related to study treatment (as judged by the core team, blinded to treatment arm) any time from the first day of study treatment until 28 days after the last study vaccine administration.

Grade 4 AEs and deaths at any time on study will be considered as a primary safety outcome.

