 - Participants who are enrolled, but who do not receive vaccination #1 will be taken off study. No further evaluations are required. These participants will be replaced.
 - Premature Treatment Discontinuation Evaluations: Participants who prematurely discontinue study treatment prior to receiving vaccination #2 or #3 should remain on study (off study treatment) until the final visit. No further vaccinations should be administered. The participants should complete the premature treatment/study discontinuation valuation as specified in the SOE. Participants should complete the safety evaluations per protocol until study completion (clinical assessments, hematology, chemistries and VRC review).
 - Premature Study Discontinuation Evaluation: Participants who discontinue the study prior to the final visit should complete the premature treatment/study discontinuation evaluations as specified in the SOE.

The analysis windows will be formed around each study visit using the midpoints between adjacent weeks as cutoffs. If there are multiple evaluations within the window for a given visit, then the evaluation closest to the scheduled study week will be used, and the earlier measurement will be used if there are two measurements which are equally distant from the scheduled week.

5 Statistical Methods

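### A related Grade 3 event in weeks 8–12 or 16–24 is a primary safety outcome only if another vaccination follows it

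*SAP*

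**What the plan says.** SAP 3.1.2 defines the primary safety outcome as at least one Grade 3 or higher adverse event, apart from short-lived injection site pain or tenderness, that the blinded core team judges possibly, probably or definitely related. The counting period is "any time from the first day of study treatment until 28 days after the last study vaccine administration". A second sentence lifts the time limit for the most severe events: "Grade 4 AEs and deaths at any time on study will be considered as a primary safety outcome". Only Grade 3 events therefore depend on the window.

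SAP 2.1 schedules four doses in every arm; for the Gag-alone and placebo arms it reads "administered by one injection/electroporation at week 0, week 4, week 12 and week 24". SAP 5.2 keeps every exposed participant in the safety analysis, including those who stop early.

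The suspension rule in SAP 2.4 uses the same outcome in both adverse-event limbs: "Two or more participants experience a primary safety outcome that is possibly or probably related to study treatment" and "One or more participants experience a primary safety outcome that is definitely related to study treatment".

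On follow-up after early stopping, SAP 4.3 says: "Participants who prematurely discontinue study treatment prior to receiving vaccination #2 or #3 should remain on study (off study treatment) until the final visit". It adds: "Participants should complete the safety evaluations per protocol until study completion". The SAP's opening section states that "the primary safety outcome data collection is completed at 48 weeks of follow-up".

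**The concern.** The end of the window moves with the number of doses received, and two of the three planned dosing intervals are longer than 28 days. For an event that starts late in such an interval, whether it counts is settled afterwards by whether another dose is given. Two participants with the same event on the same day, judged equally related, can be classified differently.

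The dosing decision may itself respond to the event. Where it does, the events that fall out of the outcome are those that led to stopping, and the reported percentage errs on the low side. The suspension rule inherits the problem: when a gap event occurs, nobody can yet say whether it is a primary safety outcome.

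**Working it through.** The plan states no figure on this point to reproduce. The check is day arithmetic on its own schedule.

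**Inputs.** Doses at weeks 0, 4, 12 and 24, that is days 0, 28, 84 and 168 (SAP 2.1). Window end = day of last dose + 28 (SAP 3.1.2). Arms of 20, 10 and 10 (SAP 2.1). Ordinary visit window ±14 days; COVID-19 allowances of +60 and then +180 days, with +90 encouraged (protocol 6.2.3, SAP 4.3).

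**Window end by last dose received.**
- #1 only: 0 + 28 = day 28
- #2: 28 + 28 = day 56
- #3: 84 + 28 = day 112
- #4: 168 + 28 = day 196

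**Conditional days**, on which a related Grade 3 event counts only if a later dose follows: max(0, next dose day − previous dose day − 28).
- #1 to #2: 28 − 0 − 28 = 0
- #2 to #3: 84 − 28 − 28 = 28 (weeks 8–12)
- #3 to #4: 168 − 84 − 28 = 56 (weeks 16–24)
- Total: 84 of 168 days (50%)

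**Example.** A related Grade 3 event starts 40 days after #3, on day 84 + 40 = 124. If #4 is given, the window runs to day 196 and the event counts. If #4 is not given, the window closed on day 112 and it does not.

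**Delays** (assuming the dose is given at the delayed visit).
- #2 14 days late (day 42): a gap of 42 − 28 = 14 days opens after #1. If #3 stays on schedule, the next gap shrinks to 84 − 42 − 28 = 14, so the total stays at 84.
- #4 late: the gap after #3 is 56 days plus the delay, that is 70 (+14), 116 (+60), 146 (+90) or 236 (+180) days.

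**Effect of one lost event on the SAP 5.2 estimate** (exact binomial 95% CI).

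| Arm size | Event counted | Event not counted |
|---|---|---|
| 20 | 1/20 = 5% (0.1–24.9%) | 0/20 = 0% (0–16.8%) |
| 10 | 1/10 = 10% (0.3–44.5%) | 0/10 = 0% (0–30.8%) |

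**Suspension rule.** One participant with a definitely related primary safety outcome is a complete trigger, as are two participants with possibly or probably related ones. SAP 2.4 applies at any time during the study, but the event must still meet the 3.1.2 definition. A Grade 3 event in a gap therefore has no settled status under these limbs until the next dose is given or ruled out.

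**Residual gap under the example fix** (window to the later of day 196 and last dose + 28): max(0, day of #4 − 196). On the nominal schedule this is 0. For #4 at +14, +60, +90 and +180 days (days 182, 228, 258 and 348) it is 0, 32, 62 and 152 days. Hence the supportive count to the week 48 visit.

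**The case against.** Several points on the other side stand.

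- **Wording.** SAP 3.1.2 does not say whether the last administration is the last one received or the scheduled fourth. The second reading would remove the problem on the nominal schedule. The first is the plain one, and nothing in the text reviewed fixes the window end for participants who stop early.
- **Cause.** A reader might infer that Grade 3 toxicity stops vaccination and so the safety result is biased. The documents do not say that Grade 3 events end vaccination; SAP 4.3 only foresees early stopping.
- **Narrow conditions.** The outcome is binary. An event is lost only if it is Grade 3, judged related, starts more than 28 days after the latest dose, follows no earlier qualifying event, and is followed by no further dose. A participant stopped by a related Grade 3 event within 28 days of a dose already counts.
- **Calendar time is not risk.** The 50% figure is a share of days, and it would be wrong to read it as half of events lost. Nor is the shorter window after fewer doses a loss in itself, since it partly reflects less exposure.
- **Other safeguards.** A reader might infer that such an event would pass unnoticed. SAP 2.4 has the SMC review adverse events and treatment discontinuations by arm, and it lets a review be convened for any identified concern. SAP 6 lists overall safety separately. These reduce the risk but correct neither the primary percentage nor the pre-specified limbs.
- **48-week data collection.** This does not contradict the 28-day window, because Grade 4 events and deaths need follow-up throughout.
- **Follow-up.** SAP 4.3 names stopping before #2 or #3. Follow-up after stopping before #4, which concerns the longer gap, has to be inferred from the 48-week duration in SAP 2.1.

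**Conclusion.** The point holds in a limited form. Followed as written, the definition classifies identical related Grade 3 events by a decision taken after them, over 84 of the 168 days to dose 4 on the nominal schedule and over more if #4 is late. This is a flaw in the counting rule, beyond a missing detail. It rests on reading the last administration as the last dose received.

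The direction of error is towards a lower percentage when an event contributes to stopping. Its size cannot be estimated from the documents. In arms this small a single event moves the estimate from 5% or 10% to zero, which shows sensitivity and does not forecast a bias. The documents do not support saying that the primary safety result is biased, or that the suspension rule fails. They do support saying that an event's status under both adverse-event limbs can be unknown at onset. The change is worth making before analysis.

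**What to change.** In SAP 3.1.2 and 5.2, make the analysis window independent of whether later doses are given. One workable form: for every vaccinated participant, count related Grade 3 or higher events from first vaccination through the later of week 28 (28 days after the scheduled fourth dose) and 28 days after the last dose received. Relatedness stays with the blinded core team, and the sentence on Grade 4 events and deaths stays. Report the count through the week 48 visit as a supportive analysis, to cover the residual gap when #4 is late. Making week 48 the primary window for everyone is not needed: it would add late events in completers that the plan now leaves out.

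The sponsor must also reconcile SAP 2.4, 3.1.2 and 4.3. Because 2.4 borrows the definition, the sponsor should state how the suspension rule relates to the revised analysis window, so that the rule is not changed by default. SAP 4.3 should state the follow-up after stopping before #4. The content of the suspension rule is for the sponsor.

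Cost: wording in the SAP and in the protocol outcome section it cites (10.2.1), agreed and dated before unblinded results are seen. For participants who stop before #2 or #3 the safety data are already planned; for those who stop before #4 this needs confirming. A few late events judged possibly related may be added, so the reported percentage may be slightly higher.

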3.2 Secondary Outcome Measures

Per protocol Section 10.2.1, the secondary outcome measures are as follows:

1. The number of CEs with a CD4 T cell response at week 26 compared to baseline in an individual study participant.
2. The number of CEs with a CD8 T cell response at week 26 compared to baseline in an individual study participant.
3. The total magnitude of CD4 T cell responses against each CE added together in each study arm at week 26 compared to baseline.
4. The total magnitude of CD8 T cell responses against each CE added together in each study arm at week 26 compared to baseline.

4 Statistical Principles

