5.1 Analysis of the Primary Immunogenicity Objective

The planned analysis will compare $Y = \text{sum of CEs recognized by CD4 and CD8 T cells at week 26 minus the number at baseline}$ between the p24CE/full-length Gag DNA and placebo arm, using a two-sided 5% level Wilcoxon rank-sum test, which is anticipated to have greater statistical power than analyzing the binary version of whether $Y > 0$, for which statistical power was based.

An exact 95% confidence interval (CI) for the median of all paired differences between observations in the two arms (i.e., Hodges-Lehmann estimate) will be calculated to provide additional insight on the effect of p24CE/full-length Gag DNA vaccine. Comparisons will also be made between the Gag DNA alone vaccine arm and each of the other arms in the same manner.

The primary immunogenicity analysis for this pilot study will be per protocol, limited to participants who received all four study vaccination/placebo administrations and who did not take any medication prohibited by the study protocol on or prior to their week 26 visit. Since the amount of missing data is expected to be low in this study, the primary comparison will be based on the complete case analysis, i.e., remove records with missing data.

The following sensitivity analyses will be carried out to measure the robustness of the study findings:

- Using the stratified Wilcoxon (Van Elteren) test adjusting for the stratification factor.
- Using modified ITT approach for the primary comparison.
- Excluding the data from participants with delayed #2 and/or #3 vaccination injection due to the COVID -19 pandemic.

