5.3 Analysis of the Secondary Objectives

The percentage of participants in each study arm with a CD4 and/or CD8 cell response to an increased number of CEs at week 26 compared to baseline will be presented along with an exact binomial 95% CI. Pairwise comparisons among study arms will be conducted using Fisher's exact test. Similar analyses will be performed for CD4 and CD8 cell responses separately.

The absolute change in total magnitude of CD4 T cell responses against each CE added together among study arms will be compared using the two-sided Wilcoxon rank-sum test. The analysis for CD8 T cell responses will be conducted in the same manner. All statistical tests will be two-sided at the 5% nominal level of significance without adjustment for multiple testing.

6 Report components

Detailed descriptions of the content of each of the following sections are given in the AIP.

1. Study entry
 - a. Screening
 - b. Accrual
 - c. Eligibility and stratification errors
2. Baseline characteristics
3. Protocol deviations
4. Study and treatment status
5. Primary immunogenicity outcome
 - a. Evaluability
 - b. Primary immunogenicity outcome
 - c. Sensitivity analyses
6. Safety:
 - a. Primary safety outcome
 - b. Deaths
 - c. Overall safety
7. Secondary Outcomes

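### The CD4 and CD8 secondary outcomes are defined as numbers of CEs but compared between arms only as the percentage with any increase, so lineage-specific count change has no estimate, interval or test

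*SAP*

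**What the plan says.** SAP 3.2 words secondary outcomes 1 and 2 as counts per participant: "The number of CEs with a CD4 T cell response at week 26 compared to baseline in an individual study participant" and "The number of CEs with a CD8 T cell response at week 26 compared to baseline in an individual study participant". Outcomes 3 and 4 are the total CD4 and CD8 magnitudes.

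The matching objectives in SAP 2.3.2 are worded as percentages: "To compare the percent of individual study participants in each study arm with a CD4 T cell response to an increased number of CEs", and for CD8 "To compare the percent of individual study participants in each study arm with a CD8 T cell response to an increased number of CEs". Objective 1 asks the same of the combined CD4 and/or CD8 response.

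SAP 5.3 follows the objectives. It presents the percentage with an increase in the combined response, with an exact binomial interval, and then: "Pairwise comparisons among study arms will be conducted using Fisher's exact test". For the lineages it adds: "Similar analyses will be performed for CD4 and CD8 cell responses separately". The Wilcoxon test in 5.3 is reserved for magnitude: "The absolute change in total magnitude of CD4 T cell responses against each CE added together among study arms will be compared".

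The primary outcome in 3.1.1 is also a number of CEs at week 26 compared to baseline, for CD4 and CD8 summed. SAP 5.1 analyses its change by Wilcoxon rank-sum test with a Hodges-Lehmann estimate and exact 95% interval, for all pairs of arms. It describes that test as one "which is anticipated to have greater statistical power than analyzing the binary version of whether" the change exceeds zero.

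**The concern.** Two outcomes worded like the primary receive a different kind of analysis, and no reason is given. Once a lineage's count change is reduced to increased or not, a gain of one CE and a gain of five are the same result.

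Two things are at stake:

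- **Interpretation.** The primary variable sums CD4 and CD8 recognition, so the natural follow-up is which lineage produced any difference. A Hodges-Lehmann shift in number of CEs cannot be set beside a percentage with any increase, because the scales differ.
- **Reporting.** The SAP's opening section says it covers the outcomes for the primary manuscript and ClinicalTrials.gov. If 5.3 is followed as written, the only between-arm result for outcomes 1 and 2 is a percentage, whereas their definition is a number.

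**Working it through.** **Step 1. Line up objective, outcome and analysis in the SAP.**

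| Quantity | Objective (2.3) | Outcome (3.1, 3.2) | Between-arm analysis (5.1, 5.3) |
|---|---|---|---|
| Combined count change | Primary 1 | Primary | Wilcoxon, Hodges-Lehmann, exact CI |
| Combined, any increase | Secondary 1 | none | Fisher |
| CD4 count change | none | Secondary 1 | none |
| CD4, any increase | Secondary 2 | none | Fisher |
| CD8 count change | none | Secondary 2 | none |
| CD8, any increase | Secondary 3 | none | Fisher |
| CD4, CD8 magnitude | Secondary 4, 5 | Secondary 3, 4 | Wilcoxon |

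Only the first and last rows agree across all three columns. The CD4 and CD8 count changes are outcomes without an analysis. The three binary increases are analysed without being listed as outcomes.

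**Step 2. Reproduce the plan's power.** Inputs from SAP 2.1: 20 v 10 in each two-arm comparison, 10% allowance, two-sided 5% Fisher test, 0.64 v 0.10 and 0.85 v 0.30. Evaluable numbers are 20 × 0.9 = 18 and 10 × 0.9 = 9; overall, 36 / 0.9 = 40. Power is the sum, over all x and y, of Bin(x; 18, p1) × Bin(y; 9, p2) for tables with Fisher p ≤ 0.05.

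- 0.64 v 0.10: 79.8%
- 0.85 v 0.30: 79.4%

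Both agree with the stated 80%. No figure in the plan is disputed.

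**Step 3. What the choice of test does to power.** The documents give no distribution of CE gains, and their design rates are not specific to CD4 or CD8, so every row below is an assumption. Each was simulated at 18 v 9, comparing a two-sided Wilcoxon test on count change with Fisher on any increase. Gains are numbers of CEs among those who increase, first arm v second. Ranges show the spread over repeated runs.

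| Proportion increasing | Assumed gains | Wilcoxon | Fisher |
|---|---|---|---|
| 0.85 v 0.30 | 1 + Poisson(1) in both, 10% losses in both | 0.58 | 0.79 |
| 0.85 v 0.30 | 1 + Poisson(1) in both, no losses | 0.70–0.71 | 0.80–0.81 |
| 0.64 v 0.30 | 1 + Poisson(1) in both, no losses | 0.31 | 0.34 |
| 0.64 v 0.10 | 1 in both, no losses | 0.80 | 0.80 |
| 0.85 v 0.30 | 1–4 v 1–2, no losses | 0.95 | 0.79 |
| 0.64 v 0.30 | 1 + Poisson(2) v 1 + Poisson(0.3), losses 4% v 10% | 0.60–0.62 | 0.34–0.36 |
| 0.64 v 0.40 | 2–4 v 1, no losses | 0.63 | 0.19 |
| 0.64 v 0.64 | 2–4 v 1, no losses | 0.40–0.42 | 0.03–0.04 |

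The pair 0.64 v 0.30 is illustrative; it is not one of the plan's design contrasts. In the sixth row the mean gains are 1 + 2 = 3 and 1 + 0.3 = 1.3 CEs.

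Where gain sizes are equal, Fisher matches or beats Wilcoxon, even without losses. Where gains are larger on vaccine, Wilcoxon is usually the stronger. In the last row the arms differ only in how many CEs are gained, and Fisher has essentially no power.

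**The case against.** The strongest defence is that 5.3 is an analysis of the secondary objectives and does what objectives 2 and 3 ask. The 3.2 entries can be read as the underlying measurement, with 5.3 supplying the summary. On that view, rewording outcomes 1 and 2 as the proportion with an increase would settle the matter without new tests. This stands as the minimum repair of the wording, but it would still leave lineage-specific count change unestimated.

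A reader might infer more than the documents support:

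- **That CD4 and CD8 have no between-arm analysis.** They do: the dichotomised versions are compared pairwise. Only the count is not.
- **That breadth is thrown away.** Combined breadth is kept in the primary analysis, and magnitude is compared by lineage. The loss is confined to CD4-only and CD8-only count change.
- **That the SAP rejects the binary version and then contradicts itself.** 5.1 says only that the rank test is expected to be more powerful. A count primary with binary secondaries is a coherent choice.
- **That the binary test always costs power.** Step 3 shows that it can be the stronger test.

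Two limits also stand. The SAP takes its outcomes from protocol section 10.2.1 and leaves table detail to the Analysis Implementation Plan. Neither was available, and count summaries by lineage may be specified there. These are also unadjusted secondary analyses in a 40-person pilot; no primary or safety conclusion depends on them.

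**Conclusion.** The point holds as a misalignment. As the SAP is written, secondary outcomes 1 and 2 receive no estimate, interval or comparison on the scale on which they are defined, and secondary objective 1 has no listed outcome. This follows from the text and needs no assumption beyond the absence of a remedy in the two sources not seen.

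The effect on power is assumption-dependent, so it is not the main argument. The substantive loss is that a lineage-specific difference in how many CEs are gained could go unseen when similar proportions gain at all. The primary inference is untouched. The change is worth making because it is cheap and lets the lineage results be read on the primary outcome's scale.

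**What to change.** 1. In 5.3, add for CD4 and CD8 separately the method of 5.1: Wilcoxon rank-sum test on change in number of CEs from baseline to week 26, Hodges-Lehmann estimate and exact 95% interval, pairwise between arms.
2. Keep the percentages, exact intervals and Fisher comparisons for secondary objectives 1 to 3. Report both analyses, since neither test is uniformly stronger.
3. In 3.2, list the binary increases (combined, CD4, CD8) as outcomes, so that each analysis has a named outcome.
4. Check the wording against protocol section 10.2.1 and the Analysis Implementation Plan.

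Cost: no new data, and the method is already planned for the primary outcome. It adds at most 2 lineages × 3 pairs of arms = 6 secondary p-values. Section 5.3 already leaves its tests unadjusted, so the added results should be read mainly through their estimates and intervals.
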